5.3. Method for Assigning Subjects to Treatment Groups

The subject will be randomly assigned to one of two study groups: 800 µg vaginal misoprostol (group 1) or 800 µg vaginal misoprostol preceded by 200 mg mifepristone orally (group 2). Randomization will be performed through a central randomization process using REDCAP. Participants will be randomized in a 1:1 ratio of treatment groups. Randomization will be stratified by research center.

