7.1. Sample Size Determination

Sample size calculations are based on detecting differences in the success rates between the misoprostol only and combined groups. Based upon prior research, we would expect a 60-71% single-dose success rate in the misoprostol only group [25]. Our preliminary data showed a 90% single-dose

success rate in the combined group using the proposed study regimen [11]. If we assume a conservative 85% success rate estimate for combined (C) and 70% success in the misoprostol only (M), we require 134 participants/group to show a difference if one is there (Table 2). To arrive at the total number of women needed to enroll, we inflate this estimate by 10% for loss to follow-up (5%) and interim analysis (5%). We will have adequate power to show a difference in success rates for all proportions above 10%. Thus, our proposed recruitment goal of 300 women (150/group) will enable us to find a clinically meaningful difference of 15% and confidently find the expected difference (20%) between groups.

Combination success rate	Misoprostol only success rate				
	50%	60%	65%	70%	75%
80%	n = 45 C: ±11.7% M: ±14.6%	n = 91 C: ±8.2% M: ±10.1%	n=151 C: ±6.4% M: ±7.6%	n = 313 C: ±4.4% M: ±5.1%	n = 1134 C: ±2.2% M: ±1.7%
85%	n = 33 C: ±12.2% M: ±17.1%	n = 57 C: ±9.3% M: ±12.7%	n=83 C: ±7.7% M: ±10.3%	n = 134 C: ±6.8% M: ±7.8%	n = 270 C: ±4.2% M: ±5.1%
90%	n = 25 C: ±11.8% M: ±19.6%	n = 38 C: ±9.5% M: ±15.6%	n=51 C: ±8.2% M: 13.1%	n = 72 C: ±6.9% M: ±10.6%	n = 113 C: ±5.5% M: ±8.0%
95%	n = 18 C: ±10.3% M: ±23.8%	n = 26 C: ±8.4% M: ±19.2%	n = 31 C: ±7.7% M: ±17.0%	n = 42 C: ±6.5% M: ±14.0%	n = 55 C: ±5.8% M: ±11.5%

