Logistic regression and classification and regression trees (CART) will be used to develop a predictive model for successful management of early pregnancy failure, which will serve as the basis for a clinical predictive index [66-68]. Our group has used this methodology with success [69,70]. Initially the predictive model will only include biomarkers, and then both biomarkers and epidemiologic and clinical characteristics will be considered in the predictive model. The sensitivity of the predictive index (i.e., proportion of patients with success who are defined as “high chance of success” by the rule) will be of primary interest [71]. The negative predictive value will also be calculated using the derived sensitivity and specificity with the population prevalence of success. This value is also of clinical interest.

For model building, we will enter all biomarkers that will have shown in the bivariate analysis at least borderline associations with the endpoints of interest ($p < 0.20$), as well as interaction terms that are suggested by the results of the explanatory model. Terms will then be removed from the model using a backward elimination procedure, removing factors which cause an insignificant change in the sensitivity of the model. To test the change in sensitivity between models (with and without the variables), we will use McNemar’s test. In particular, we will be comparing the proportion of correctly classified cases of success between models. The rule would involve calculating a score for each person, based on the actual values of the regression coefficients. The goal is to utilize all variables that improve the sensitivity of the model. Unlike the explanatory model, whose goal is to determine which variables are associated with success, the predictive models will be developed in order to determine which combination of variables best predicts the outcome. Additionally, variables and interactions included in the model must be biologically plausible.

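### Logistic prediction model: terms are dropped only on change in sensitivity, with no cut-off or specificity fixed, so classification of failures plays no part in variable selection

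*Combined protocol and SAP*

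**What the plan says.** Section 7.2 (Statistical Methods) sets out the logistic prediction model as follows.

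- **Primary measure.** Sensitivity is the share of women with treatment success who are classed as having a high chance of success "by the rule) will be of primary interest". Negative predictive value is also to be calculated, as a further quantity of clinical interest.
- **Entry.** Biomarkers with a bivariate p below 0.20 enter, plus interactions suggested by the explanatory model.
- **Elimination.** Backward elimination removes terms whose effect on sensitivity is not significant. The comparison is McNemar's test on the proportion of successes classified correctly with and without the term.
- **Goal.** "The goal is to utilize all variables that improve the sensitivity of the model".

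No probability cut-off, and no minimum or fixed specificity, is given for these comparisons.

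Elsewhere, section 7.2 plans sensitivity, specificity and both predictive values for each single biomarker, with ROC curves for cut-offs. It also plans ROC comparison of simplified scores with fuller models and of CART with the logistic model, one CART tree built for sensitivity and another for specificity, and bootstrap validation of the prediction rule.

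**The concern.** Sensitivity looks only at women who succeed. With nothing held fixed among the failures, it can always be raised by moving the threshold, and it reaches 100% when no woman is classed as likely to fail. Used as the only criterion for retaining a term, it has two defects. It ignores any gain in recognising failures, and its answer depends on where the threshold happens to sit, which the plan does not say.

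The secondary objective in section 2 is a model to guide individual counselling and treatment choice. Section 1.2 motivates the markers with levels that differed in women in whom misoprostol failed. A selection step blind to failures can discard such markers from the logistic model and from the simplified scores derived from it.

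**Working it through.** **Inputs from the documents**

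- Success rates (section 7.1): "If we assume a conservative 85% success rate estimate for combined (C) and 70% success in the misoprostol only (M"). Allocation (section 5.3): "Participants will be randomized in a 1:1 ratio of treatment groups".
- Pooled success = (0.70 + 0.85)/2 = 0.775. In 300 women that is 232.5 successes and 67.5 failures.
- Range: section 7.1 also says "we would expect a 60-71% single-dose success rate in the misoprostol only group" and cites 90% from preliminary data on the combination. Pooled success then runs from (0.60 + 0.85)/2 = 0.725 to (0.71 + 0.90)/2 = 0.805.
- Analysed number: 300 × 0.95 = 285, using the 5% loss to follow-up in section 7.1.

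**The plan's own figure.** Section 7.1 says "we require 134 participants/group to show a difference if one is there". Assume a two-sided 5% level and 80% power (section 7.1 states neither):

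- n = [1.96√(2 × 0.775 × 0.225) + 0.8416√(0.70 × 0.30 + 0.85 × 0.15)]² / 0.15² = (1.1575 + 0.4889)² / 0.0225 = 120.5, or 121.
- With continuity correction: (120.5/4) × [1 + √(1 + 4/(120.5 × 0.15))]² = 133.5, or 134.

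This reproduces 134, so 70% and 85% are the rates behind the design.

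**The limiting rule.** If every woman is classed as high chance, sensitivity = 232.5/232.5 = 100%, specificity = 0/67.5 = 0%, accuracy = 77.5%, and negative predictive value is 0/0, undefined. Sensitivity is at its maximum here whatever the success rate.

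**Assumptions for the simulation.** The documents give no marker strengths and no cut-off. Each marker is taken as normal with unit SD and a mean shift d between outcomes, so AUC = Φ(d/√2); d = 0.75 gives 0.70 and d = 1.0 gives 0.76. Accuracy is apparent, from the fitted model. McNemar's test is exact, at two-sided 5%.

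**One marker, cut-off 0.5, 77.5% success, 285 women**

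| AUC | Sensitivity | Specificity |
|---|---|---|
| 0.60 | 0.998 | 0.01 |
| 0.70 | 0.976 | 0.11 |
| 0.76 | 0.958 | 0.24 |
| 0.86 | 0.943 | 0.47 |

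For the AUC-0.70 marker, sensitivity and specificity are 0.932 and 0.229 at 70% success, and 0.994 and 0.045 at 85% success.

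**The planned comparison: model with and without a second marker** (the first marker has AUC 0.70)

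| Second marker | Cut-off | Sensitivity | Specificity | McNemar better | McNemar worse |
|---|---|---|---|---|---|
| AUC 0.70 | 0.5 | 0.98 to 0.96 | 0.11 to 0.27 | 0% | 26% |
| AUC 0.70 | success rate | 0.65 to 0.70 | 0.65 to 0.71 | 37% | 0% |
| AUC 0.76 | 0.5 | 0.977 to 0.947 | 0.11 to 0.37 | 0% | 39% |
| AUC 0.76 | success rate | 0.647 to 0.735 | 0.646 to 0.736 | 71% | 0% |

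The percentages move by a few points between sets of runs; another set gave 29% in place of 26% and 42% in place of 37%. A likelihood-ratio test at 5% retains the second AUC-0.70 marker in about 100% of runs. An AUC-0.70 marker also passes the p < 0.20 entry screen in essentially every run, so the screen does not explain the difference.

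At cut-off 0.5 the change is non-significant in 100 − 26 = 74% of runs for the AUC-0.70 marker, and the rule removes it. In the other 26% the change is significant but in the wrong direction: read literally the term stays, but this contradicts the stated goal.

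**With specificity held at 50% (illustrative).** The second marker raises sensitivity from 0.77 to 0.86 (AUC 0.70) or 0.89 (AUC 0.76). Better markers now score better, and the rule that classes everyone as high chance no longer qualifies.

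**The case against.** Three arguments stand against the point.

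1. **The plan does look at failures elsewhere.** Single-marker specificity and predictive values, negative predictive value of the index, the ROC comparisons and the specificity-oriented tree all use them. This stands in part. A reader might infer that a worthless index could be presented as nearly perfect; the documents do not support that, because an index with zero specificity would have an undefined negative predictive value and a poor ROC curve. A marker dropped from the logistic model may also still enter CART, which screens separately on AUC above 0.6. But these analyses act on single markers, on CART or on finished rules. None restores a term to the logistic model, and the simplified scores inherit the loss.

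2. **The direction depends on the cut-off.** This stands. A reader might infer that markers of failure always score worse on sensitivity. They do so at 0.5 in these simulations; near the success rate, or at fixed specificity, they score better. Nor is the high success rate what makes the all-high-chance rule maximal, since that is true at any prevalence; it only makes a 0.5 cut-off behave almost like that rule. The cut-off dependence is itself part of the defect.

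3. **Favouring sensitivity is a legitimate value choice.** The objective is to predict who will succeed, and avoiding the mislabelling of likely successes is defensible. This stands as a reason to report sensitivity prominently. It does not justify sensitivity with nothing fixed alongside it as the only test for keeping a term.

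**Conclusion.** The point holds as a weakness in a stated rule of the secondary prediction analysis. In section 7.2, logistic terms are kept or dropped on sensitivity alone, failures play no part in that step, and the outcome depends on a cut-off that is not given. Even at the more favourable cut-off examined, the success rate, an informative second marker of AUC 0.70 is kept in about 37% of runs, against about 100% with a likelihood-ratio test; at 0.5 it is never kept for improving sensitivity.

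These sizes rest on assumed marker strengths, normal markers independent within outcome group, two illustrative cut-offs, 285 women and 77.5% success. The logical part (sensitivity alone can be raised by giving up specificity) needs none of these assumptions. The change should be made, but it does not bear on the randomised comparison of the two regimens.

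**What to change.** In the model-building paragraphs of section 7.2:

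- Keep or drop logistic terms by likelihood-ratio test or AIC instead of McNemar's test on change in sensitivity, and reword the goal sentence to match.
- Judge the index primarily on bootstrap-validated AUC.
- Report sensitivity together with specificity at an operating point fixed in advance, for example specificity at 90% sensitivity. This preserves the priority given to recognising successes.

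ROC curves and bootstrap validation are already planned, so the cost is wording in the statistical section, with no new data. The downside is that the headline accuracy figure may look less favourable than an unconstrained sensitivity would.

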The highly effective, safe combination regimen described above may also effectively treat women with EPF [11,12,39,58]. Our preliminary observations [11] strongly support this. However, this regimen needs to be rigorously tested in a sufficiently powered clinical trial [5]. The biologic basis for why a combination regimen should be more effective and safe than misoprostol alone, even in the cases of a failed pregnancy, has been preliminarily described. We and others have hypothesized that those failed pregnancies that do not respond to uterine evacuation with misoprostol alone appear to represent a subset of EPF in which the invasion of the extravillous trophoblast into the decidualized endometrium is altered [24,59]. This enhanced "attachment" of the pregnancy may be due to a direct trophoblastic effect, and/or may be due to characteristics of the decidualized endometrium. There is evidence for a direct supportive effect of P_4 on human trophoblast function [60], and therefore, this effect could be inhibited by the use of mifepristone. In addition, mifepristone also has anti-glucocorticoid activity, with relatively high binding affinity for the glucocorticoid receptor [20,21]. Since glucocorticoids are critical to

the function of human trophoblast cells [61], the presence of mifepristone could lead to decreased proliferation, differentiation, and/or invasive properties of the trophoblast – even in a failed pregnancy [62].

2 Study Objectives

Primary Objective

To compare the effectiveness of combination treatment (mifepristone premedication plus single-dose misoprostol) to single-dose misoprostol (standard of care) for the management of early pregnancy failure.

Our hypothesis states that the combination of mifepristone and single-dose misoprostol will be more effective than single-dose misoprostol alone, and will reduce the proportion of failed medical treatments (those who require repeat dosing or surgery) by at least 20% in 300 women seeking treatment for first trimester embryonic/fetal demise and anembryonic gestation.

Secondary Objective

[figure not shown]
To test the ability of trophoblastic and endometrial biomarkers to predict which women are most likely to succeed with medical management of early pregnancy failure and to derive and internally validate a prediction model designed to guide individualized counseling and treatment for early pregnancy failure.

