To be useful, a clinical rule must be easily applied. In order to ensure easy understanding and unhindered application, the variables and parameters comprising the predictive score will be simplified with two methods: 1) by recalculating the predictive score using values of the coefficients, rounded to the nearest integer, and 2) by calculating the score simply as the sum of the dichotomous independent variables identified by the model. (It will be necessary, for this approach to recode continuous predictors as dichotomous variables.) This will result in the most parsimonious model. The performance of the new rules will then be compared with that of more complete models using ROC curves. We plan to evaluate potential cutoffs of each marker to optimize our ability to distinguish among successes and failures.

We will also approach our predictive modeling using CART. Candidates that have an individual area under the curve (AUC) > 0.6 will be considered. CART is useful in identifying complex relationships between biomarkers and clinical outcomes. These analyses recursively split observations into two

groups (nodes), t_L and t_R , based on the covariate that maximizes a given split function. In the case of a continuous outcome, a commonly used split function is the reduction in sums of squares error, i.e. the amount of variability explained by the split. The best split is defined to be the one that best predicts the response where the best predictor is defined to be the one that maximizes the split function. All splits of the observations in each of the resulting nodes are then considered and the best split identified. This process is repeated recursively until a stopping rule is achieved (e.g. no further splits exist with greater than 5 observations in each of the resulting nodes). We will employ 10-fold cross-validation to assess the significance of the resulting tree as described in Breiman [72]. The sensitivity and specificity of the CART versus logistic model will be compared using ROC curves, to determine the best predictive rule for management success. CART software will be used to evaluate combinations of biomarkers creating a tree maximizing sensitivity and a tree maximizing specificity. Data will be combined into a three-tiered algorithm to maximize accuracy.

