The prediction rule will be internally validated with a “bootstrap” approach [73-78]. With this approach, a large number of samples are taken from the original data (with replacement) and the predictive accuracy is tested in each of these samples. Sampling with replacement generates a population identical in composition to the observed sample. This method provides a relatively unbiased estimate of the test characteristics of the predictive rule [78].

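### One of the two planned simplified scores, an unweighted count of predictors split at data-optimised cut-offs, can lose up to about 9 points of AUC, and the planned checks understate that loss.

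*Combined protocol and SAP*

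**What the plan says.** Section 2 (Study Objectives) sets as the secondary objective to derive and "internally validate a prediction model designed to guide individualized counseling and treatment for early pregnancy failure".

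Section 7.2 builds a logistic model and then simplifies its score in two ways:

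- **Method 1:** "1) by recalculating the predictive score using values of the coefficients, rounded to the nearest integer".
- **Method 2:** "by calculating the score simply as the sum of the dichotomous independent variables identified by the model". Of this method the section adds: "It will be necessary, for this approach to recode continuous predictors as dichotomous variables".

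On cut-offs the section says: "We plan to evaluate potential cutoffs of each marker to optimize our ability to distinguish among successes and failures". It gives no values, no selection criterion and no separate data. On the comparison of rules it says: "The performance of the new rules will then be compared with that of more complete models using ROC curves".

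Validation is by bootstrap, in which "a large number of samples are taken from the original data (with replacement) and the predictive accuracy is tested in each of these samples". The section presents this as giving a nearly unbiased picture of performance. It does not say that cut-offs are re-chosen or the model refitted in each resample.

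The same section also plans a CART rule with tenfold cross-validation, a CART-versus-logistic comparison, lowess plots of each marker's shape, and separate models by arm. It names sensitivity as the main performance measure. It does not say which score becomes the final index.

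**The concern.** Method 2 discards two kinds of information: the gradient of risk on either side of each cut-off, and the relative strength of the markers. The reason given is ease of use. Weighted integer points over a few bands can also be added by hand, and the count saves no assay.

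The second problem is that the checks favour the count. A cut-off tuned to the trial's outcomes raises the count's AUC in those same data, so a same-data ROC comparison can show the simple rule level with the full model when it is worse in new women. At stake is the quality of an index meant for individual counselling. If the count were preferred because it looked as good, the index could separate successes from failures worse than the data allowed.

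**Working it through.** **Inputs from the documents.** Section 7.1: 300 women, 150 per group; 85% and 70% success; 5% loss to follow-up. Mean success is (85 + 70)/2 = 77.5%, so failures are 22.5%: about 68 of 300, or 64 of 285.

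**The plan's own figure.** Section 7.1 gives 134 per group. The two-proportion formula (two-sided 0.05, 80% power, continuity-corrected; the power is inferred) gives 133.5, rounded up to 134. This figure concerns the primary comparison. The documents give no AUC, marker effect or precision target for the score, so the sizes below rest on assumptions.

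**Assumptions.** Normal markers; a difference of d SD between successes and failures; a linear logit; correlation 0 or 0.3.

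**Definitions.** AUC = P(success scores higher than failure) + ½ P(tie). Loss = AUC(continuous weighted score) − AUC(count). Hidden share = 1 − same-data loss / true loss.

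**Hand check, three independent markers at d = 0.5.**

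- Continuous score with known weights: Φ(√(3 × 0.25)/√2) = Φ(0.612) = 0.730.
- Count with each cut midway between the groups: each marker is positive with probability Φ(0.25) = 0.599 in successes and 0.401 in failures. The count 0, 1, 2, 3 then has probabilities 0.065, 0.289, 0.432, 0.215 in successes, and the reverse in failures. AUC = 0.542 + ½ × 0.277 = 0.680.
- The loss is 5.0 points even with well-placed cuts, so it comes from the form of the score and not only from noisy cut-offs.

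**Simulation at n = 285.** 18 scenarios with 3 to 6 markers, 200 trials each, cut-offs by the Youden index, true AUC in 40,000 new subjects. Losses are in AUC points; they were averaged before rounding.

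| Markers (d) | Correlation | True AUC, continuous vs count | True loss | Same-data loss | Hidden |
|---|---|---|---|---|---|
| 0.5 ×3 | 0 | 0.721 vs 0.673 | 4.7 | 0.2 | 96% |
| 0.8, 0.4, 0.2 | 0 | 0.736 vs 0.662 | 7.4 | 1.6 | 78% |
| 0.7, 0.5, 0.3, 0.2, 0.1 | 0 | 0.735 vs 0.658 | 7.7 | 0.2 | 97% |
| 1.0, 0.3, 0.3 | 0.3 | 0.756 vs 0.666 | 9.0 | 4.1 | 54% |
| 0.4 ×4 | 0.3 | 0.642 vs 0.632 | 1.0 | −2.5 | all |
| 0.3 ×5 | 0.3 | 0.599 vs 0.600 | −0.1 | −3.6 | no loss to hide |

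Over the nine independent-marker scenarios the true loss was 3.4 to 8.9 points; over the nine with correlation 0.3 it was −0.1 to 9.0. For per-arm models (142 to 150 women, independent markers) the true loss was 4.7 to 7.8, while the same data showed −2.9 to +0.3.

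**Simulation at n = 300, independent markers.**

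- 0.4 ×3: true 0.681 vs 0.640; same data 0.696 vs 0.702. All of the loss is hidden.
- 0.3, 0.5, 0.8: true 0.753 vs 0.686 (6.7 points); same data 0.763 vs 0.738 (2.5). Hidden: 1 − 2.5/6.7 = 63%.
- 0.2, 0.4, 0.9: true 0.757 vs 0.676 (8.1 points); same data 0.765 vs 0.731 (3.4). Hidden: 1 − 3.4/8.1 = 58%.

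**Bootstrap.** Testing a fixed rule in resamples of the data that built it returns, on average, its same-data performance. In eight scenarios it gave the same-data loss to within 0.1 point. Repeating the cut-off search and refit in each resample did better:

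| Markers, correlation | Same-data loss | Loss after full-repeat bootstrap | True loss |
|---|---|---|---|
| 0.8, 0.4, 0.2; 0 | 2.2 | 5.9 | 7.5 |
| 0.7, 0.5, 0.3, 0.2, 0.1; 0 | 0.4 | 4.8 | 7.4 |
| 0.5 ×3; 0.3 | −1.6 | 0.8 | 2.5 |

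**Alternative score.** Integer points over sample fifths, weighted by coefficient, gave true AUCs of 0.670, 0.741 and 0.744 in the three n = 300 cases. In that run the full score gave 0.680, 0.753 and 0.757, and the count 0.640, 0.686 and 0.676. The share of the loss recovered is 0.030/0.040 = 75%, 0.055/0.067 = 82% and 0.068/0.081 = 84%.

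**The case against.** - **The count is not the chosen index.** A reader might infer that the bedside tool will be the count. The documents do not support this: it is one of two simplifications, CART is also planned, and no adoption rule is stated. This stands.
- **A fixed loss cannot be quoted.** A reader might take 3 to 8 points as the cost. No document figure supports it, and only 10 of the 18 scenarios fall in that range. Shape matters too: with step-shaped effects (four settings simulated) the count beat a linear continuous score in new patients by 0.4 to 1.4 points. The planned lowess plots could reveal such shapes. This stands, so the size must be conditional.
- **The ROC comparison is not blind.** With unequal markers, where the loss tends to be largest, it usually shows some of it. *Understates* is the right word in general; near-complete masking is typical of equal markers.
- **Internal validation is planned.** True, and the analysts may intend a bootstrap that repeats model building. The text describes only testing the rule in each resample, and that version does not reveal the loss. The tenfold cross-validation is attached to the CART tree.
- **Method 1 is available.** It is not a safe fallback as written. Rounding sets coefficients below 0.5 in size to zero; with markers on an SD scale, true AUC fell by 1 to 13 points.
- **AUC is not the plan's main measure.** Section 7.2 gives that place to sensitivity, and the loss in sensitivity has not been sized here. This stands.

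**Conclusion.** The concern holds in conditional form. Under normal, linear-effect markers with about 300 women and 22.5% failures, the count costs roughly 0 to 9 points of true AUC: about 3 to 9 with independent markers, less with equal correlated ones, and possibly nothing if effects are step-shaped. The same-data ROC comparison hides nearly all of the loss for equal markers. For the unequal sets shown it hides 54% to 97%, and about 60% in the two n = 300 cases. The bootstrap, as section 7.2 describes it, shares this blindness, so the section's assurance of near-unbiasedness does not hold for a rule whose cut-offs were tuned on the same data.

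A reader might go further and infer that the trial's main conclusion or its size is in doubt. It is not: the primary comparison and the 300 women are untouched, and only the secondary prediction objective is affected.

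**What to change.** 1. **Validation (section 7.2, bootstrap paragraph).** State that variable selection, the choice of cut-offs or bands, and the assignment of points are repeated in every bootstrap sample. Compare the simplified, full and CART rules on optimism-corrected AUC and on optimism-corrected sensitivity. The correction is partial: in the three scenarios checked it recovered 5.9 of 7.5, 4.8 of 7.4 and 0.8 of 2.5 points.
2. **Score (section 7.2, method 2).** Replace the count with, or at least place beside it, integer points weighted by the coefficients over bands fixed in advance (for example sample fifths), with no search for a single best cut-off per marker. Keep the markers continuous in the underlying model, in the shape that the lowess plots suggest.

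The cost is plan wording, a little more programming, and a scoring card with several bands per marker instead of one yes/no. No new data are needed.

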Once all participant phlebotomy specimens have been obtained, we will be able to derive a predictive model for successful medical management vs. failure for all subjects. Separate predictive models will then be built for each treatment arm, and any differences found here will lay foundations for future research. Accurate assessment of gestational age (GA) can be a challenge in women who present with EPF, and GA may in fact be a confounder in the relationship between hormone levels and the nature of the demise. Depending on time of presentation relative to time of demise, biomarker levels may be more a reflection of the actual GA, or may in fact be impacted by duration of demise (i.e. β hCG, P_4 may start declining after demise occurs). We can utilize last menstrual period dating (LMP) with the caveat that LMP is not always certain. To overcome this measurement error problem, we will also analyze a

subset of women with a sure LMP and for whom ultrasound dating is consistent with LMP. If the model for this subset is consistent with the model for the full data, or GA is not found to significantly modify the relationship, only the full data model will be presented.

Biomarker levels will be summarized overall, and by treatment group, using standard descriptive statistics. We will use graphical methods, such as lowess smoothers, to determine the shape (linear or non-linear, potential cut-points for classifying levels) of the relationship between the biomarker level and probability of success, and subsequently for inclusion as predictors in a multivariable logistic model. We will analyze a subset of women with a sure LMP and for whom ultrasound dating is consistent with LMP separately for the most accurate analysis of the relationship between biomarker concentration and the characterization of an EPF that will respond well to medical management. We can compare this definitive LMP group to the group of women in whom LMP is unsure. We will calculate the sensitivity, specificity, and positive and negative predictive values for each biomarker. The predictive accuracy of different cutoffs will be evaluated using ROC curves.

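### Biomarker cut-offs are chosen from the trial's own outcomes, per-marker accuracy is reported without correction for that choice, and the planned bootstrap as described would not remove the optimism

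*Combined protocol and SAP*

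**What the plan says.** All of the relevant text is in section 7.2.

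- **Finding cut-points.** Smoothed plots are to be used to "determine the shape (linear or non-linear, potential cut-points for classifying levels) of the relationship between the biomarker level and probability of success", and the result feeds the choice of predictors for a multivariable logistic model. Also: "The predictive accuracy of different cutoffs will be evaluated using ROC curves".
- **Per-marker accuracy.** "We will calculate the sensitivity, specificity, and positive and negative predictive values for each biomarker". No correction for a data-chosen cut-off is mentioned.
- **Screening.** For model building, "we will enter all biomarkers that will have shown in the bivariate analysis at least borderline associations with the endpoints of interest", at p < 0.20. The text does not say whether the marker is continuous or two-level at this step.
- **Simplification.** One version of the clinical score is a sum of two-level variables: "It will be necessary, for this approach to recode continuous predictors as dichotomous variables". The same paragraph ends: "We plan to evaluate potential cutoffs of each marker to optimize our ability to distinguish among successes and failures".
- **Validation.** The CART tree gets 10-fold cross-validation. The prediction rule gets a bootstrap in which accuracy is evaluated in each resample, and the plan describes the result as close to unbiased. It does not say that the cut-off search, the screen or the elimination steps are redone in each resample.

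Separate models are also planned for each treatment arm, so some of this work will be done in about 150 women.

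**The concern.** A cut-off picked because it best separates successes from failures in one set of women will look better in those women than in new ones. Even a marker unrelated to outcome has some cut-off at which it seems to discriminate. Sensitivity and specificity read at that cut-off are therefore too high on average.

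The hypotheses in section 2 concern a single biomarker as well as combinations, so the per-marker figures are part of the answer to the secondary objective. The resulting score is meant to guide individual counselling and treatment. If apparent accuracy is reported as it stands, a marker with no predictive value can be presented as useful, and a real marker will look stronger than it is. The planned bootstrap is the safeguard a reader would rely on, so it matters whether it corrects for the search.

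**Working it through.** **1. Fixing the sample size and number of failures.** The plan gives no figure for cut-off optimism, so the inputs come from section 7.1: 85% against 70% success and 134 per group. That figure reproduces with two-sided alpha 0.05, 80% power (both inferred) and a continuity correction.

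- n0 = [1.96 × √(2 × 0.775 × 0.225) + 0.842 × √(0.70 × 0.30 + 0.85 × 0.15)]² / 0.15² ≈ 120.5, which rounds up to 121.
- With continuity correction: n = (n0/4) × [1 + √(1 + 4/(n0 × 0.15))]² ≈ 133.5, which rounds up to 134, as stated.

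With 300 women (150 per group), expected failures are:

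- Pooled: 300 × (1 - 0.775) = 67.5, taken as 68.
- Misoprostol alone: 150 × 0.30 = 45.
- Combination: 150 × 0.15 = 22.5, taken as 23.

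**2. Apparent accuracy of a noise marker.** The measure is Youden's J = sensitivity + specificity - 1, which is 0 for a useless marker. A continuous marker was simulated independently of outcome. The cut-off with the largest J was chosen, and J was read in the same women (10,000 simulated trials per setting).

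| Setting | Mean apparent J, inner 80% of values searched | Range, inner 50% to inner 90% searched |
|---|---|---|
| 300 women, 68 failures | 0.116 | 0.110-0.116 |
| 150 women, 45 failures | 0.148 | 0.141-0.149 |
| 150 women, 23 failures | 0.187 | 0.179-0.188 |

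A separate simulation of 4,000 trials, choosing the cut by the largest chi-square, gave 0.117, 0.148 and 0.191 (22 failures in the last case). It also took a real marker shifted by 0.4 SD in 300 women: apparent J averaged 0.213 against a true 0.145 at the chosen cut, an excess of 0.213 - 0.145 = 0.068.

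**3. What the bootstrap does.** Two versions were run on 300 noise datasets with 200 resamples each, searching the inner 80%.

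- *As described:* keep the chosen rule and average its J over resamples. Each resample is drawn from the original women, so this average returns the apparent value by construction.
- *Search repeated:* in each resample choose a new cut-off, then set optimism = mean of [J of that rule in the resample - J of that rule in the original data], and corrected J = apparent J - optimism.

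| Setting | Apparent J | Fixed rule retested | Optimism | Corrected J |
|---|---|---|---|---|
| 300 / 68 | 0.114 | 0.114 | 0.079 | 0.035 |
| 150 / 45 | 0.149 | 0.149 | 0.099 | 0.050 |
| 150 / 23 | 0.186 | 0.187 | 0.124 | 0.062 |

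The 95% interval from the fixed-rule version lay wholly above 0 in 42%, 42% and 36% of noise datasets.

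**4. Conditional check on p-values.** If a two-level marker at its best cut were given an ordinary one-degree-of-freedom p-value, a noise marker would reach p < 0.05 in about 44-45% of trials (300 women, inner 80% searched). Coarser searches give 21% (deciles) and 9% (quartiles). With the marker kept continuous, the rate is about 5%, and it passes p < 0.20 in 20%.

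**The case against.** The strongest reply is that the plan never says it tests or screens two-level markers. The only general rule for continuous variables in section 7.2 is a t-test or rank test. Two-level recoding is called necessary only for the sum score, which is described after model selection, so predictors may still be continuous until then. Terms are dropped by change in sensitivity with McNemar's test, not by a p-value at a chosen cut.

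That stands. A reader might infer that noise markers will usually pass the p < 0.20 screen, or that nearly half will be declared significant. The documents do not support either. The lowess sentence allows cut-points to be set before modelling, but no text states that two-level markers are screened or given p-values. A false-positive rate across several markers would also need an assumed number of independent markers, and the plan's list is open-ended.

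Three further points carry some weight:

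- Validation is planned, and the cut-offs used in the simplified score belong to the rule that is bootstrapped. The per-marker accuracies, however, are not mentioned as covered.
- The sponsor may intend a full optimism-corrected bootstrap. The text describes only testing accuracy in each resample. If more is intended, the remedy for that part is wording.
- An exhaustive search is more aggressive than reading a plot or an ROC curve. A coarser choice would give less optimism, though not none. The sizes above depend on this.

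**Conclusion.** The concern holds for accuracy estimates. Cut-offs are tuned and judged on the same outcomes, per-marker sensitivity, specificity, PPV and NPV carry no stated correction, and the bootstrap as described would hand back the apparent accuracy.

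Under an inner-80% search, a useless marker shows a mean J of about 0.12 with all 300 women and 0.15 to 0.19 within an arm. Repeating the search in each resample removes roughly two thirds of this. A small residue (0.035-0.062) remains, so the correction is good but not perfect.

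The figures assume a continuous marker without ties, unrelated to outcome; the success rates of section 7.1; and full data on 300 women. Narrowing the search to the inner 50% changes J little. Inflated p-values follow only if two-level markers at data-chosen cuts are tested, which the plan leaves open and should settle.

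The point is confined to the secondary biomarker objective. The primary comparison of the two regimens is unaffected.

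**What to change.** Change section 7.2 in three places.

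1. **Screening and modelling paragraphs.** State that biomarkers enter the bivariate screen and the logistic model as continuous variables, and that all association p-values come from that form.
2. **Per-marker accuracy.** Report AUC with a confidence interval for each marker. Give sensitivity, specificity, PPV and NPV at a data-chosen cut-off only after optimism correction.
3. **Bootstrap paragraph.** In every bootstrap sample, repeat the whole process: cut-off search, p < 0.20 screen, backward elimination and score simplification. Apply each resample's rule to the original data, subtract the mean optimism, and report the corrected accuracy as the result.

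The cost is SAP wording and slightly more code, with no new data. Reported accuracies will be lower.
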